**Table 5. Infusion Reaction Treatment Guidelines**

NCI CTCAE Grade	Treatment	Premedication at subsequent dosing
Grade 1  Mild reaction; infusion interruption not indicated; intervention not indicated	Increase monitoring of vital signs as medically indicated until the subject is deemed medically stable in the opinion of the investigator.	None
Grade 2  Requires infusion interruption but responds promptly to symptomatic treatment (e.g., antihistamines, NSAIDS, narcotics, IV fluids); prophylactic medications indicated for <=24 hrs	
Stop Infusion and monitor symptoms.
 
Additional appropriate medical therapy may include but is not limited to:
 
 
IV fluids
 
Antihistamines
 
NSAIDS
 
Acetaminophen
 
Narcotics
 
 
Increase monitoring of vital signs as medically indicated until the subject is deemed medically stable in the opinion of the investigator.
 
If symptoms resolve within one hour of stopping drug infusion, the infusion may be restarted at 50% of the original infusion rate (e.g., from 100 mL/hr to 50 mL/hr). Otherwise dosing will be held until symptoms resolve and the subject should be premedicated for the next scheduled dose.
 
Subjects who develop Grade 2 toxicity despite adequate premedication should be permanently discontinued from further trial treatment administration.
	
Subject may be pre-medicated 1.5h (<math>\pm</math> 30 minutes) prior to infusion of pembrolizumab (MK-3475) with:
 
Diphenhydramine 50 mg po (or equivalent dose of antihistamine).
 
Acetaminophen 500-1000 mg po (or equivalent dose of antipyretic).

Grades 3 or 4  Grade 3:  Prolonged (i.e., not rapidly responsive to symptomatic medication and/or brief interruption	
Stop Infusion.
 
Additional appropriate medical therapy may include but is not limited to:
 
 
IV fluids
 
Antihistamines
 
	No subsequent dosing

NCI CTCAE Grade	Treatment	Premedication at subsequent dosing
of infusion); recurrence of symptoms following initial improvement; hospitalization indicated for other clinical sequelae (e.g., renal impairment, pulmonary infiltrates)  Grade 4: Life-threatening; pressor or ventilatory support indicated	NSAIDS Acetaminophen Narcotics Oxygen Pressors Corticosteroids Epinephrine  Increase monitoring of vital signs as medically indicated until the subject is deemed medically stable in the opinion of the investigator.  Hospitalization may be indicated.  Subject is permanently discontinued from further trial treatment administration.	

Appropriate resuscitation equipment should be available in the room and a physician readily available during the period of drug administration.

## 5.8 Diet/Activity/Other Considerations

### 5.8.1 Diet

Subjects should maintain a normal diet unless modifications are required to manage an AE such as diarrhea, nausea or vomiting.

### 5.8.2 Contraception

Pembrolizumab may have adverse effects on a fetus in utero. Furthermore, it is not known if pembrolizumab has transient adverse effects on the composition of sperm. For this trial, male subjects will be considered to be of non-reproductive potential if they have azoospermia (whether due to having had a vasectomy or due to an underlying medical condition).

Female subjects will be considered of non-reproductive potential if they are either:

(1) Postmenopausal (defined as at least 12 months with no menses without an alternative medical cause; in women < 45 years of age a high follicle stimulating hormone (FSH) level in the postmenopausal range may be used to confirm a post-menopausal state in women not using hormonal contraception or hormonal replacement therapy. In the absence of 12 months of amenorrhea, a single FSH measurement is insufficient.);

OR

(2) Have had a hysterectomy and/or bilateral oophorectomy, bilateral salpingectomy or bilateral tubal ligation/occlusion, at least 6 weeks prior to screening;

OR

(3) Has a congenital or acquired condition that prevents childbearing.

Female and male subjects of reproductive potential must agree to avoid becoming pregnant or impregnating a partner, respectively, while receiving study drug and for 120 days after the last dose of study drug by complying with one of the following:

(1) Practice abstinence† from heterosexual activity;

OR

(2) Use (or have their partner use) acceptable contraception during heterosexual activity.

Acceptable methods of contraception are‡:

- Single method (one of the following is acceptable):
  - Intrauterine device (IUD)
  - Vasectomy of a female subject's male partner
  - Contraceptive rod implanted into the skin
- Combination method (requires use of two of the following):
  - Diaphragm with spermicide (cannot be used in conjunction with cervical cap/spermicide)
  - Cervical cap with spermicide (nulliparous women only)
  - Contraceptive sponge (nulliparous women only)
  - Male condom or female condom (cannot be used together)
  - Hormonal contraceptive: oral contraceptive pill (estrogen/progestin pill or progestin-only pill), contraceptive skin patch, vaginal contraceptive ring, or subcutaneous contraceptive injection

†Abstinence (relative to heterosexual activity) can be used as the sole method of contraception if it is consistently employed as the subject's preferred and usual lifestyle and if considered acceptable by local regulatory agencies and ERCS/IRBs. Periodic abstinence (e.g., calendar, ovulation, symptothermal, post-ovulation methods, etc.) and withdrawal are not acceptable methods of contraception.

‡If a contraceptive method listed above is restricted by local regulations/guidelines, then it does not qualify as an acceptable method of contraception.

Subjects should be informed that taking the study medication may involve unknown risks to the fetus (unborn baby) if pregnancy were to occur during the study. In order to participate in the study subjects of childbearing potential must adhere to the contraception requirement (described above) from the day of study medication initiation (or 14 days prior to the initiation of study medication for oral contraception) throughout the study period up to 120 days after the last dose of trial therapy. If there is any question that a subject of childbearing potential will not reliably comply with the requirements for contraception, that subject should not be entered into the study.

### **5.8.3 Use in Pregnancy**

If a subject inadvertently becomes pregnant while on treatment with pembrolizumab, the subject will immediately be removed from the study. The site will contact the subject at least monthly and document the subject's status until the pregnancy has been completed or terminated. The outcome of the pregnancy will be reported to the Sponsor and to Merck without delay and within 24 hours to the Sponsor and within 2 working days to Merck if the outcome is a serious adverse experience (e.g., death, abortion, congenital anomaly, or other disabling or life-threatening complication to the mother or newborn).

The study investigator will make every effort to obtain permission to follow the outcome of the pregnancy and report the condition of the fetus or newborn to the Sponsor. If a male subject

impregnates his female partner the study personnel at the site must be informed immediately and the pregnancy reported to the Sponsor and to Merck and followed as described above and in Section 7.3.2.

#### 5.8.4 Use in Nursing Women

It is unknown whether pembrolizumab is excreted in human milk. Since many drugs are excreted in human milk, and because of the potential for serious adverse reactions in the nursing infant, subjects who are breast-feeding are not eligible for enrollment.

### 5.9 Subject Withdrawal/Discontinuation Criteria

Subjects may withdraw consent at any time for any reason or be dropped from the trial at the discretion of the investigator should any untoward effect occur. In addition, a subject may be withdrawn by the investigator or the Sponsor if enrollment into the trial is inappropriate, the trial plan is violated, or for administrative and/or other safety reasons. Specific details regarding discontinuation or withdrawal are provided in *Other Procedures* section.

A subject must be discontinued from the trial for any of the following reasons:

- The subject withdraws consent.
- Confirmed radiographic disease progression

*Note:* For unconfirmed radiographic disease progression, please see Appendix 11.4, *RECIST 1.1 Guidelines, Confirmation of Progression*.

*Note:* A subject may be granted an exception to continue on treatment with confirmed radiographic progression if clinically stable or clinically improved; please see Appendix 11.4, *RECIST 1.1 Guidelines, Confirmation of Progression*.

- Unacceptable adverse experiences such as dose-limiting toxicities
- Intercurrent illness that prevents further administration of treatment
- Investigator's decision to withdraw the subject
- The subject has a confirmed positive serum pregnancy test
- Noncompliance with trial treatment or procedure requirements
- The subject is lost to follow-up
- Completed 12 months of uninterrupted treatment with pembrolizumab and poly-ICLC (17 administrations of combination study treatment [study diagram 2.2.2]).

*Note:* 12 months of study medication is calculated from the date of first dose. Subjects who stop combination study treatment after 12 months may be eligible for up to one year of additional study treatment if they progress after stopping study treatment, provided they meet the requirements detailed in Section 7.2.13, Second Course Phase (Retreatment Period).

- Administrative reasons

The End of Treatment and Follow-up visit procedures are listed in Section 6 (Protocol Flow Chart) and Section 7.2.12 (Visit Requirements). After the end of treatment, each subject will be followed for 30 days for adverse event monitoring (serious adverse events will be collected for 90 days after the end of treatment as described in Section 7.3). Subjects who discontinue for reasons other than progressive disease will have post-treatment follow-up for disease status until disease progression, initiating a non-study cancer treatment, withdrawing consent or becoming lost to follow-up. After documented disease progression each subject will be followed by telephone for overall survival until death, withdrawal of consent, or the end of the study, whichever occurs first.

### **5.9.1 Discontinuation of Study Therapy after CR**

Discontinuation of treatment may be considered for subjects who have attained a confirmed CR that have been treated for at least 24 weeks with pembrolizumab and had at least two treatments with pembrolizumab beyond the date when the initial CR was declared. Subjects who then experience radiographic disease progression may be eligible for up to one year of additional treatment with pembrolizumab and poly-ICLC via the Second Course Phase at the discretion of the investigator if no cancer treatment was administered since the last dose of pembrolizumab, the subject meets the safety parameters listed in the Inclusion/Exclusion criteria, and the trial is open. Subjects will resume therapy at the same dose and schedule at the time of initial discontinuation. Additional details are provided in Section 7.2.13, *Second Course Phase (Retreatment Period)*.

### **5.10 Subject Replacement Strategy**

Subjects who withdraw from therapy prior to completion of cycle 1 of therapy will be replaced during the phase I portion of the trial to allow for evaluation of at least 3 subjects at each dose level. Similarly, if patients withdraw before assessment of tumor response in the phase II portion of the trial, they will be replaced unless withdrawal is due to clinical disease progression.

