**5.4.1.2 Dose Limiting Toxicity (DLT) Criteria for poly-ICLC escalation phase:**

A DLT will be defined as any Grade  $\geq 3$  or higher treatment-related toxicity that occurs during the DLT-evaluation period. Toxicity that is clearly and directly related to the primary disease or to another etiology is excluded from this definition. The following will be DLTs, regardless of relatedness:

- Any Grade 4 irAE
- Any Grade 4 non-hematologic toxicity
- Any Grade  $\geq 3$  diarrhea or vomiting that does not resolve within 3 days
- Any Grade 3 irAE, excluding colitis or pneumonitis, which does not downgrade to  $\leq$  Grade 2 within 3 days after onset of the event despite maximal medical supportive care including systemic corticosteroids or does not downgrade to  $\leq$  Grade 1 or baseline within 14 days.
- Any  $\geq$  Grade 3 colitis irrespective of duration
- Any Grade  $\geq 3$  non-infectious pneumonitis irrespective of duration
- Liver transaminase elevation  $\geq 5 \times$  but  $\leq 8 \times$  ULN that does not downgrade to Grade 2 within 5 days after onset with optimal medical management, including systemic corticosteroids. Transaminase elevation  $> 8 \times$  ULN or total bilirubin  $> 5 \times$  ULN will be considered a DLT regardless of duration or reversibility
- Any increase in AST or ALT  $> 3 \times$  ULN and concurrent increase in total bilirubin  $> 2 \times$  ULN (Hy's Law).

The definition of DLT *excludes* the following conditions:

- Grade 3 fatigue for  $\leq 7$  days
- Grade 3 endocrine disorder (thyroid, pituitary, and/or adrenal insufficiency) that is managed with or without systemic corticosteroid therapy and/or hormone replacement therapy
- Grade 3 inflammatory reaction attributed to a local antitumor response that resolved to  $\leq$  Grade 1 within 30 days
- Concurrent vitiligo or alopecia of any AE grade
- Grade 3 infusion-related reaction (IRR; first occurrence and in the absence of steroid prophylaxis) that resolves within 6 hours with appropriate clinical management.
- Grade 3 neutropenia that is not associated with fever or systemic infection that improves by at least 1 grade within 3 days.
- Grade 3 or Grade 4 lymphopenia (unless clinically significant)
- Grade 3 thrombocytopenia that is not associated with clinically significant bleeding that requires medical intervention, and improves by at least 1 grade within 7 days

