- Isolated Grade 3 electrolyte abnormalities that are not associated with clinical signs or symptoms and are reversed with appropriate maximal medical intervention within 3 days
- Grade 3 fever lasting  $\leq 24$  hours with or without medical therapy and is not considered a serious adverse event

**The period for definition of DLT will be the first 3 weeks of treatment.** Dosing interruptions are permitted in the case of medical / surgical events or logistical reasons not related to study therapy (e.g., elective surgery, unrelated medical events, patient vacation, and/or holidays). Subjects should be placed back on study therapy within 3 weeks of the scheduled interruption, unless otherwise discussed with the Sponsor. The reason for interruption should be documented in the patient's study record.

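### Section 5.10 replaces Phase I subjects who leave therapy in cycle 1 with no exception for DLT, and nothing says a replaced DLT patient stays in the 3+3 count

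*Combined protocol and SAP*

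**What the plan says.** **Replacement.** Section 5.10 states for Phase I: "Subjects who withdraw from therapy prior to completion of cycle 1 of therapy will be replaced during the phase I portion of the trial". The purpose given is "to allow for evaluation of at least 3 subjects at each dose level". No reason for withdrawal is excepted. The next sentence, on Phase II patients who leave before response assessment, does carry an exception: "they will be replaced unless withdrawal is due to clinical disease progression".

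**Discontinuation.** Section 5.9 lists reasons for which a subject must be discontinued. One is "Unacceptable adverse experiences such as dose-limiting toxicities". It also allows a subject to "be dropped from the trial at the discretion of the investigator should any untoward effect occur".

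**Window.** Section 5.4.1.2: "The period for definition of DLT will be the first 3 weeks of treatment". Table 2 in 5.3 sets a 3-week cycle, so the DLT window and cycle 1 coincide.

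**Count.** Sections 5.4.1.1 and 8.5.1a base escalation, expansion and stopping on how many patients in a cohort experience a DLT. They require the recommended Phase II dose (RP2D) to have at least 6 enrolled patients with no more than one DLT. Neither section defines a DLT-evaluable patient or mentions replaced patients. Section 8.6 defines one analysis set: every enrolled subject who received any study medication.

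**A related mismatch.** Section 5.4.1.2 excludes from DLT a "Grade 3 infusion-related reaction (IRR; first occurrence and in the absence of steroid prophylaxis) that resolves within 6 hours with appropriate clinical management". For Grade 3 or 4 infusion reactions, Table 5 says: "Subject is permanently discontinued from further trial treatment administration".

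**The concern.** In a 3+3 design the replacement rule determines who is counted. The usual safeguard is that a patient with a DLT has already supplied the endpoint and is never replaced; replacement is for patients who leave without a DLT before the window closes. Section 5.10 omits that distinction, although its Phase II sentence shows that an exception could be written. A patient taken off on Day 8 for a DLT has not completed cycle 1 and so meets the replacement condition. Because the stated purpose is to reach a number of evaluated subjects, a site could take the replaced patient as not evaluated.

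The 3+3 count is the Phase I primary analysis and sets the dose for up to 27 Phase II patients. With cohorts of three, one uncounted DLT can change the decision, and it can do so only towards escalation.

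**Working it through.** **1. Reproduce the stated Phase I size.** Section 8.4 gives 3 to 12. The minimum is 3 (stop at level 1 after two or more DLTs in three). The maximum is 2 levels × 6 = 12. The figure reproduces, with no replacements included; any would come on top of 12.

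**2. Follow a DLT patient through the text.**
- DLT on, say, Day 8: inside the 3-week window (5.4.1.2).
- Section 5.9: the subject must be discontinued.
- Section 5.10: off therapy before cycle 1 is complete, hence replaced.
- Sections 5.4.1.1 and 8.5.1a: the patient experienced a DLT, hence should trigger expansion or stopping.

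The last two steps are joined by no rule. The difference between withdrawing (5.10) and being discontinued (5.9) does not settle it. Section 5.9 has both terms in its heading and speaks of subjects being withdrawn by the investigator, and 7.2.11 uses the two together.

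**3. Size, if DLT patients were replaced and not counted.** Inputs not in the documents, and therefore assumed: the true DLT rate p, and the share f of DLT patients replaced and uncounted.

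Level 1 is cleared with 0 DLTs in 3, or 1 in 3 followed by 0 in 3 (5.4.1.1 c to e, read as a classical 3+3):

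P(clear) = (1 − p)³ + 3p(1 − p)² × (1 − p)³ = (1 − p)³ + 3p(1 − p)⁵

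Among counted patients the DLT rate becomes q = p(1 − f)/(1 − pf), which then takes the place of p.

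- p = 0.30, f = 0: 0.343 + 0.151 = 0.494.
- p = 0.30, f = 0.5: q = 0.15/0.85 = 0.176; 0.559 + 0.201 = 0.759.
- p = 0.40, f = 0: 0.216 + 0.093 = 0.309.
- p = 0.40, f = 0.5: q = 0.20/0.80 = 0.25; 0.422 + 0.178 = 0.600.

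Over a wider range of assumed values:

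| True DLT rate | f = 0 | f = 0.25 | f = 0.50 | f = 0.75 |
|---|---|---|---|---|
| 20% | 0.709 | 0.798 | 0.887 | 0.964 |
| 33.3% | 0.428 | 0.551 | 0.709 | 0.887 |
| 40% | 0.309 | 0.428 | 0.600 | 0.828 |
| 50% | 0.172 | 0.265 | 0.428 | 0.709 |

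**4. Patients who stop in cycle 1 without a DLT.** Assume 30% have a DLT and a further 10% stop early without one. If the 10% are replaced, the counted DLT rate is 0.30/0.90 = 0.333 and level 1 clears with probability 0.428. If they are kept as DLT-free, the rate is 0.30 and it clears with probability 0.494. Under the protocol's own DLT definition, replacing this group is the stricter choice.

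**The case against.** The strongest reply is that replaced does not mean uncounted. Section 5.10 never says that a replaced subject leaves the DLT count, and a patient with a DLT has been evaluated for the Phase I endpoint. The rules in 5.4.1.1 for one DLT in three and for two or more would have nothing to act on if DLT patients were always removed. The RP2D rule, in 5.4.1.1 and again in 8.5.1a, refers to patients enrolled and patients experiencing a DLT; a replaced patient is both. Section 8.6 keeps every treated subject in the safety analysis. Section 5.4.1.1 h also lets Phase II toxicity inform the RP2D, and 5.11 allows termination for adverse reactions.

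Most of this stands. It makes counting DLTs the more natural reading and rules out treating 5.10 as an instruction to drop them. It does not close the gap: 8.6 governs analysis rather than cohort decisions, the Phase II safeguards act only after more patients have been exposed, and no sentence tells a site what to do with a DLT patient whom 5.10 says to replace.

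A reader might also infer that replacing patients who stop for toxicity short of a DLT biases the dose upward. The documents do not support that: 5.4.1.2 deliberately excludes those events, and step 4 shows that keeping such patients as DLT-free would loosen escalation. Of the possible examples, the infusion reaction is clear, because Table 5 ends all trial treatment. Grade 4 lymphopenia is weaker: 5.4.1 introduces Table 3 as rules for withholding pembrolizumab, which is given only on Day 1 of a cycle, so it is uncertain whether such a patient has left therapy in cycle 1.

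**Conclusion.** The point holds as an unresolved conflict. Sections 5.9 and 5.10 together make a DLT patient eligible for replacement, 5.4.1.1 and 8.5.1a need that patient counted, and nothing reconciles them. If DLT patients were replaced and left out, the bias would run towards escalation: from 49% to 76% clearance of 1 mg at a 30% true DLT rate, and from 31% to 60% at 40%, with an assumed replaced share of one half. The true rates and the share are illustrations, not estimates from the documents.

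A reader might go further and conclude that 5.9 removes most or all DLT patients from the count, so that any dose would clear with certainty (f = 1 gives q = 0). The text does not support this. Section 5.9 requires discontinuation and is silent on counting, and f = 1 would nullify the adjacent 3+3 rules. It is an arithmetical bound only.

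**What to change.** - **Section 5.10, mirrored in 8.5.1a:** state that a subject with a DLT in the 3-week window is DLT-evaluable, stays in the numerator and denominator, and is not replaced. Limit Phase I replacement to subjects who leave before the end of the window without a DLT.
- **Escalation review:** list subjects who stop in cycle 1 for drug-related events that 5.4.1.2 excludes from DLT, so that the reviewers see them. This does not require counting them as DLTs or as DLT-free.
- **Reconciliation:** the sponsor should reconcile the DLT exclusions in 5.4.1.2 with the discontinuation rules in Tables 3 and 5. Which clinical rule should prevail is not a matter for this review.
- **If Phase I patients have already been treated:** document how each cycle-1 withdrawal was counted.

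The cost is a few sentences. The small downside is that a cohort may expand or escalation may stop earlier, which is what the 3+3 rules intend.

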### **5.11 Clinical Criteria for Early Trial Termination**

Early trial termination will be the result of the criteria specified below:

1. Quality or quantity of data recording is inaccurate or incomplete
2. Poor adherence to protocol and regulatory requirements
3. Incidence or severity of adverse drug reaction in this or other studies indicates a potential health hazard to subjects
4. Plans to modify or discontinue the development of the study drug

In the event of Merck decision to no longer supply study drug, ample notification will be provided so that appropriate adjustments to subject treatment can be made.

